3.5.1.5. Action Taken with QWO (CCH-aaes) and Mitigation Treatments

The action taken with QWO (CCH-aaes) treatment and/or the mitigation treatment will be reported by the investigator as follows:

- Not changed
- Interrupted.
- Withdrawn.

Actions taken with QWO (CCH-aaes) will be reported separately from actions taken with mitigation treatment.

3.5.2. Vital Signs

The baseline values for vital signs (study baseline) will be those taken at Day 1 pre-dose for the by-visit analyses.

Vital signs will be analyzed for Day 1, with pre-dose value as baseline and post-baseline measurement taken approximately 30 minutes after injection. Change from baseline will be the post-baseline value minus the baseline value.

3.6. Other Parameters

3.6.1. Medical History

Medical history will be mapped to preferred term using MedDRA. All medical history terms will be reviewed by the study medical monitor to determine if any other terms should be included.

3.6.2. Prior/Concomitant Medications and Procedures

A concomitant medication is any medication with a stop date on or after the date of the first QWO (CCH-aaes) injection, or a medication reported as ongoing. A prior medication is any medication taken prior to the date of the first QWO (CCH-aaes) injection. All medications will be coded with the World Health Organization (WHO) drug dictionary, by active ingredient and WHO anatomical therapeutic chemical (ATC) classification of ingredients.

A concomitant procedure is any procedure and/or nondrug therapy with a stop date on or after the date of the first QWO (CCH-aaes) injection, or a procedure and/or nondrug therapy reported as ongoing. A prior procedure is any procedure and/or nondrug therapy administered prior to the date of the first QWO (CCH-aaes) injection. Procedures will be reported using the "Additional Concomitant Procedure/Therapy" page of the eCRF.

For all previous and concomitant medications, the following information will be collected: medication name, start date, stop date or ongoing, dose and dose unit, route of administration, frequency, indication, and whether the medication is used to treat an adverse event (Yes/No).

For all previous and concomitant procedures, the following information will be collected: description of procedure/surgery/non-drug therapy, start date, stop date or ongoing, indication, and whether the therapy/procedure is used to treat an adverse event (Yes/No).

4. ANALYSIS POPULATIONS

4.1. Safety Population

The Safety Population is defined as all subjects allocated to treatment who receive at least 1 injection of QWO (CCH-aaes) with or without mitigation treatment. All demographic and baseline characteristics, as well as safety parameters, will be summarized based on this population.

4.2. Evaluable Population

The Evaluable Population is defined as all subjects allocated to treatment who receive at least 1 injection of QWO (CCH-aaes) and have at least 1 bruising assessment after the first dose of QWO (CCH-aaes). The primary and key secondary efficacy parameters will be summarized based on this population.

5. STATISTICAL METHODS

5.1. Overview

The primary efficacy endpoint will be summarized as frequency counts and percentages based on the Evaluable Population by cohort. Mean and standard deviation (SD) will also be provided.

The secondary and supportive efficacy endpoints except for change from baseline measures will be summarized as frequency counts and percentages based on the Evaluable Population by cohort and by buttock, where appropriate. The change from baseline measures will be summarized using descriptive statistics (n, mean, SD, median, minimum and maximum).

TEAEs will be summarized as frequency counts and percentages by preferred term and by cohort. The results and change from baseline for vital signs will be summarized using descriptive statistics.

Subject listings of all data from the eCRFs as well as any derived variables will be presented.

5.2. Missing Data Handling

Missing efficacy data will not be imputed for analysis unless otherwise specified.

5.3. Subject Disposition

The number of subjects included in each study population will be summarized by cohort and overall. Subjects excluded from the Safety Population or Evaluable Population will be listed.

The number and percentages of subjects screened, enrolled, completed, and withdrawn from the study, as well as the reason for withdrawal from study will be summarized by cohort and overall. The number and percentage of screen failures will also be shown.

A listing of disposition data will be provided. Screen failure reasons will also be listed. In addition, a listing for inclusion/exclusion criteria will also be presented.

5.4. **Protocol Deviations**

Protocol deviations will be divided in categories and severity (major/minor) will be determined. Protocol deviations will not be summarized; however, a subject listing will be presented.

5.5. Demographics and Baseline Characteristics

Demographics and baseline characteristics will be summarized by cohort and overall using the Safety Population. Age, height (at Screening), body weight (at Screening), and BMI in kg/m² (at Screening) will be summarized as continuous variables using descriptive statistics (n, mean, standard deviation (SD), median, minimum and maximum).

Gender, race and ethnicity will be summarized as categorical variables using frequency counts and percentages. In addition, age group and BMI group will be summarized as categorical variables using frequency counts and percentages.

The following baseline characteristics will be summarized using frequency counts and percentages:

- CR-PCSS cellulite severity ratings for each buttock at Screening.
- Hexsel CSS Section D (laxity, flaccidity or sagging of skin) scores for each buttock at Screening.
- Skin category based on Fitzpatrick Skin Scale assessment.
- Report of tobacco and alcohol use
 - Alcohol use (Never, Current, and Former).
 - Tobacco use (Never, Current, and Former).

All demographic and baseline characteristics will be presented in subject listings.

5.6. Medical and Surgical History

Medical and surgical history, including cellulite history and previous treatments, will be coded using MedDRA. Medical and surgical history data will not be summarized; however, a subject listing will be provided.

5.7. Efficacy Evaluation

Efficacy parameters will be summarized for each mitigation group based on the Evaluable Population, unless otherwise stated. Missing values will not be imputed, and only observed data will be summarized.

For mitigation treatments that are bilaterally administered (e.g. compression garments in cohort 2), efficacy parameters will be compared to the control arm (cohort 1). For mitigation treatments that are unilaterally applied (e.g. instant cold packs, arnica patches, INhance, and PDL treatment in cohorts 3-6, which are applied to the right buttock only), subjects will serve as their own control. In these cases, efficacy parameters from mitigation treatment (right buttock) will be compared to contralateral buttock with no mitigation treatment (left buttock). There will be no formal comparison of efficacy parameters between mitigation treatments.

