1.3. Schedule of Assessments

	Screening Period	Treatment Period							Follow-up Period
Procedures	Day -14	Day 1 (Baseline)	Day 2	Day 4	Day 7	Day 14	Day 22 (±3d)	Day 43 (±3d)	Day 71//ET (+ 7d)
Informed consent	X								
Inclusion/Exclusion criteria	Х								
Medical history/surgical history/cellulite history including previous treatments	Х								
Prior/Concomitant medications/procedures (including all prior medications/procedures for cellulite)	X	x	x	х	x	x	x	х	х
Physical examination (including height)	Х								
Weight	Х								Х
Fitzpatrick skin type	Xa								
Vital signs	Х	Xp							
Digital photography ^c		Х	Х	Х	Х	Х	Xd	Xd	Х
Cohort assignment	Xe								
QWO (CCH-aaes) administration		Х					Х	Х	
Subject Assessments									
Subject-Bruising Improvement Scale (S-BIS)			x	х	х	х	Xď		
Patient Bother by Bruising Scale ⁹				Х	Х		Xd		
Investigator Assessments				•	•	•			
Hexsel Cellulite Severity Scale (CSS) Subsection D	Xh								
Clinician Reported Photonumeric Cellulite Severity Scale (CR-PCSS)	Xi								
Selection and marking of dimples to be treated within both buttocks		Xc					Xd	Xq	
Investigator Assessment of Bruising Severity Scale		x	х	х	х	х	Xq		
Investigator- Bruising Improvement Scale (I-BIS) ^j			Х	Х	х	Х	Xď		

	Screening Period		Treatment Period						Follow-up Period
Procedures	Day -14	Day 1 (Baseline)	Day 2	Day 4	Day 7	Day 14	Day 22 (±3d)	Day 43 (±3d)	Day 71//ET (+ 7d)
Investigator- Global Aesthetic Improvement Scale (I-GAIS)							Xď	Х	Х

	Screening Period			Treatm	ent Per	iod			Follow-up Period
Procedures	Day -14	Day 1 (Baseline)	Day 2	Day 4	Day 7	Day 14	Day 22 (±3d)	Day 43 (±3d)	Day 71//ET (+ 7d)
Mitigation Treatment Cohorts									
Compression garments			X ^{k,p}						
Instant cold packs to the right buttock only		X ^{I,p}							
Arnica patches (OcuMend [®]) to the right buttock only		X ^{m, p}							
INhance Post-Injection Serum with TriHex Technology [®] to the right buttock only			X ^{n,p}						
Pulse dye laser (PDL) treatment to the right buttock only			X ^{o,p}						
Injection site reactions/local tolerability in each buttock treated		х	Х	х	х	Х	х	х	Х
Adverse events (AEs)		Xq							

^a Subjects with a Fitzpatrick skin rating of I-III will be included.

^b Before injection and approximately 30 minutes after injection. Pulse and blood pressure should be collected after the subject has been sitting for 5 minutes.

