4.3. Justification for Endpoints

The primary endpoint will be the investigator's assessment of bruising based on observed, inperson assessments during the first treatment session. The subject will not be able to directly view the bruised skin (ie, would have to use reflection in the mirror) and lighting may not be standardized. As such subject viewing of the bruise might be less authentic than direct viewing by the investigator.

The effect of mitigation treatments that are bilaterally administered (eg, compression garments) will be evaluated by the investigator by comparing bruising on each buttock (both of which receive mitigation treatment) vs bruising observed in the control arm (Cohort 1) that is not receiving mitigation treatment. Subjects in this group will not be able to compare their bruising to bruising on buttocks with no mitigation.

The effect of unilaterally applied (right buttock only) topical mitigation treatments (ie, arnica patches, INhance, PDL treatment) will be assessed by comparing the bruising in the mitigation-treated buttock to the contralateral buttock that did not receive mitigation treatment. As such, in unilateral mitigation treatment cohorts, subjects will serve as their own control.

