6.3. Measures to Minimize Bias

This is an open label study, however, the mitigation treatment for each subject will be assigned in a 1:1:1:1:1:1 ratio using a Mitigation Treatment Assignment Table. To ensure a balanced approach in the application of mitigation treatments and the assessment of bruising among the sites and investigators, 1-3 subjects per site will be assigned to each mitigation treatment (pending site capabilities, subjects available, and available mitigation equipment).

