6.3.1. Mitigation Treatment Assignment Table

At Screening, the investigator or designee will refer to the Mitigation Treatment Assignment Table to determine which mitigation treatment should be administered.

The investigator must maintain a subject master log linking the subject identification number to the subject's name. The subject identification number will not be reassigned to another subject in this study in the case of study withdrawal. The investigator must follow all applicable privacy laws in order to protect a subject's privacy and confidentiality. Information that could identify a subject will be masked on material sent to and/or received by the sponsor.

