2.7.4. Investigator Bruising Improvement Scale (I-BIS)

On Days 2, 4, 7, 14, and 22 (before injection), the investigator will rate the bruising of the mitigation-treated buttock when compared to the untreated (with mitigation treatment) buttock using the 3-point Likert scale (Table 6). Scores on the higher end of the range indicate greater improvement of bruising with treatment.

Table 6:Investigator Bruising Improvement Scale (I-BIS)

Rating	Response Option
1	Worse (more bruising)
2	Similar
3	Improved (less bruising)

The I-BIS evaluations will be based on live assessments while the subject is in front of the investigator. Note that the I-BIS assessment cannot be completed for subjects that either do not receive mitigation treatment (Cohort 1) or subjects that receive bilateral mitigation treatment (as in Cohort 2), as there is no untreated buttock for comparison.

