2.8. Subject Assessment Ratings

2.8.2. Subject Bruising Improvement Scale (S-BIS)

On Days 2, 4, 7, 14, and 22 (before injection), the subject will rate the bruising of the mitigationtreated buttock when compared to the untreated (with mitigation treatment) buttock using the 3-point Likert scale (Table 8). Scores on the higher end of the range indicate greater improvement of bruising with treatment.

Table 8:Subject Bruising Improvement Scale (S-BIS)

Rating	Response Option	
1	Worse (more bruising)	
2	Similar	
3	Improved (less bruising)	

Note that the S-BIS assessment cannot be completed for subjects that either do not receive mitigation treatment (Cohort 1) or subjects that receive bilateral mitigation treatment (as in Cohort 2), as there is no untreated buttock for comparison.

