5.7.2. Primary Endpoint and Secondary Endpoints – Bruising Level

For each cohort, results at each level of bruising on the Investigator Assessment of Bruising Severity Scale (see section 2.7.1) will be summarized by visit and by buttock for each subject using counts and percentages. Results and changes from baseline evaluation rating will also be summarized using descriptive statistics (mean and SD).

A listing of Investigator Assessment of Bruising Severity ratings will be provided.

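### In Cohorts 3-6 mitigation always goes on the right buttock, so right versus left cannot separate mitigation from a side difference: not at all on I-BIS and S-BIS, and on severity and Patient Bother only through data the SAP does not use

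*SAP*

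**What the plan says.** Protocol 4.3 introduces "The effect of unilaterally applied (right buttock only) topical mitigation treatments" and compares each treated buttock with the untreated one on the other side. The schedule of assessments (Protocol 1.3) fixes the side treatment by treatment, for example "Instant cold packs to the right buttock only". SAP 5.7 carries this into the analysis: for Cohorts 3-6 the treatments are those "which are applied to the right buttock only), subjects will serve as their own control", with right as mitigated and left as unmitigated. The same section uses Cohort 1 only as the comparator for bilateral compression (Cohort 2) and plans no formal comparison between mitigation treatments.

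The table decides treatment, not side. Under Protocol 6.3.1, "the investigator or designee will refer to the Mitigation Treatment Assignment Table to determine which mitigation treatment should be administered". The section on minimising bias (Protocol 6.3) seeks balance across sites, where "1-3 subjects per site will be assigned to each mitigation treatment", and does not mention side.

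The scales differ in which cohorts supply them:

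- **I-BIS** (SAP 2.7.4): "I-BIS assessment cannot be completed for subjects that either do not receive mitigation treatment (Cohort 1") or that receive bilateral mitigation (Cohort 2).
- **S-BIS** (SAP 2.8.2): "S-BIS assessment cannot be completed for subjects that either do not receive mitigation treatment (Cohort 1") or that receive bilateral mitigation.
- **Bruising severity**, the primary measure at Day 4 (SAP 5.7.2): the "Investigator Assessment of Bruising Severity Scale (see section 2.7.1) will be summarized by visit and by buttock", in every cohort. (The bruising scale is in fact described in SAP 2.7.3.)
- **Patient Bother** (SAP 5.7.4): also by buttock in every cohort.

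**The concern.** A subject is a fair control for herself only if, without mitigation, her two buttocks would bruise and be rated alike on average. The plan equalises the number of injections on Day 1 and tabulates the left-right difference in that number. It does not balance which side is injected first, how an injector works on each side, or how a rater scores each side. Because the mitigated side never varies, any constant difference of that kind is added to the apparent effect of all four unilateral treatments, in the same direction.

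Right versus left is the only planned control for four of the five mitigation treatments, and a larger sample would not reduce such a bias. On I-BIS and S-BIS the rating is itself a comparison of the two sides, so a side difference would read directly as improvement or worsening with mitigation.

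**Working it through.** **1. Inputs.** From the documents: 6 cohorts x 8 = 48 subjects, which reproduces the planned total. Unilateral cohorts: 4 x 8 = 32 of the 5 x 8 = 40 subjects planned to receive mitigation. Expected loss: 48 to about 45 evaluable, 3/48 = 6.25%. No SD, effect size or power is stated, so every size in scale grades below is an assumption.

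**2. What the data can separate.** Let D be the right-minus-left score, s a constant side difference and t_c the effect of mitigation in cohort c. Then E[D] = s + t_c in Cohorts 3-6 and E[D] = s in Cohort 1.

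- I-BIS and S-BIS: Cohorts 3-6 only. Five parameters (s and four t_c), design-matrix rank 4. Side and mitigation cannot be separated.
- Severity and Patient Bother: adding Cohort 1 gives rank 5, so separation is possible.
- The contrast in SAP 5.7 is the within-cohort D alone, with expectation s + t_c. As planned, it is fully confounded on every scale. I-GAIS, also rated by buttock in all cohorts, is in the same position as severity.

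**3. Severity, with no mitigation effect.** Assume the right scores d = 0.25 grade lower. With k of n subjects mitigated on the right, the bias in favour of mitigation is d(2k - n)/n:

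- 8 right, 0 left: 0.25
- 4 right, 4 left: 0
- 5 right, 3 left: 0.25 x 2/8 = 0.06
- 4 right, 3 left (one subject lost from 4/4): 0.25 x 1/7 = 0.04

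**4. I-BIS, with no mitigation effect.** Assume a normal latent difference with SD 0.7-1.0, rated similar when within 0.5 grade. P(improved) = 1 - Phi((0.5 - d)/SD); P(worse) = Phi((-0.5 - d)/SD).

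| d | SD 0.7: improved / worse | SD 1.0: improved / worse |
|---|---|---|
| 0.1 | 0.284 / 0.196 | 0.345 / 0.274 |
| 0.25 | 0.360 / 0.142 | 0.401 / 0.227 |
| 0.5 | 0.500 / 0.077 | 0.500 / 0.159 |

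With 4/4 sides at d = 0.25, improved and worse are equal: (0.360 + 0.142)/2 = 0.251 and (0.401 + 0.227)/2 = 0.314.

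**5. A second I-BIS model.** Assume 20% of ratings are similar and 60%, 70% or 80% of the rest favour the right for side reasons alone. Expected improved is 48%, 56% or 64%, against 40% with no side effect. The binomial chance of at least 5 of 8 improved is 0.32, 0.50 or 0.69, against 0.17. With 4/4 sides it is 0.17, 0.16 or 0.14. With 40% similar, the fixed-side chances are 0.12, 0.21 and 0.32, against 0.06.

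**6. Cohort 1 as a side reference for severity.** Take the SD of D as 0.7-1.0. The SE of s is SD/sqrt(8) = 0.25-0.35; times t(7) = 2.365, the 95% half-width is 0.59-0.84 grade. Pooling Cohorts 1 and 2 (n = 16, t(15) = 2.131, SE = SD/4) gives 0.37-0.53, if compression leaves the side difference unchanged.

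Mean squared error of one cohort's mitigation effect at d = 0.25:

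| Approach | Formula | SD 0.7 | SD 1.0 |
|---|---|---|---|
| Side fixed, as planned | d^2 + SD^2/8 | 0.124 | 0.188 |
| Cohort 1 subtracted | SD^2/8 + SD^2/8 | 0.122 | 0.250 |
| Cohorts 1+2 subtracted | SD^2/8 + SD^2/16 | 0.092 | 0.188 |
| Side split 4/4 | SD^2/8 | 0.061 | 0.125 |

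**7. Precision of the 4/4 split.** The SE stays at SD/sqrt(8) = 0.354 x SD, the same as the planned contrast. Subtracting Cohort 1 gives 0.500 x SD (+41%); subtracting Cohorts 1 and 2 gives 0.433 x SD (+22%).

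**The case against.** The strongest reply is that the whole effect is hypothetical. The side shift, the SDs and the band for similar appear in neither document. The plan also does more than match injection counts: both buttocks need the same cellulite rating and a laxity score of 0 or 1, dimple numbers should be similar, Day 1 dose is identical, injection volume is fixed, and severity has a Day 1 baseline by buttock. The Prescribing Information and Study Operations Manual, not available here, may standardise technique and scoring. In a multicentre study, side habits may differ between injectors and partly cancel. The study is open-label and descriptive, and randomising side would leave injector and rater expectation untouched.

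Most of this is fair as a limit on size. It does not restore separability: the listed controls equalise dose and starting condition, and nothing in these documents balances injection order, technique or rating by side.

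Three narrower points stand:

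- On severity and Patient Bother, partial confounding describes what the collected data could separate; the planned contrast is fully confounded there too.
- Cohort 2 can add to the side reference. At d = 0.25, subtracting the pooled estimate is better than or equal to no correction, provided compression does not alter the side difference.
- The missing paired output is a modest gap for severity. Its shell prints left and right means, so with complete pairs only the SD of the difference is absent. The Patient Bother shell has counts only.

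**Conclusion.** The concern holds. Mitigation and right side coincide in all 32 planned unilateral subjects. On I-BIS and S-BIS they cannot be separated by any analysis of the planned data. On severity and Patient Bother they could be separated only imprecisely, and the SAP does not attempt it.

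The bias equals whatever the constant side difference is, and that is unknown. For assumed shifts of 0.1-0.5 grade with no mitigation effect, I-BIS would show 28-50% improved and 27-8% worse. These figures rest on a side effect constant across subjects and on the assumed SD and band. The sample-size figure is unaffected. The point should be addressed because the remedy is cheap; confidence is medium because no side effect has been shown.

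**What to change.** **Preferred.** Have the sponsor's assignment table also randomise the mitigated side in Cohorts 3-6, as near as possible to 4 right and 4 left per cohort. Amend the text that restricts mitigation to the right, and label outputs as mitigated and unmitigated. This removes bias from a constant side effect, with no extra subjects and no loss of precision. It does not remove open-label expectation, and with 1-3 subjects per treatment per site it cannot guarantee balance within each injector.

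Cost: one column in a table that is already issued, plus a protocol amendment with IRB approval, because the right-only wording recurs in the protocol, schedule, SAP and shell footnotes. Home application of arnica and serum carries a small risk of wrong-side use; the mitigation eCRF page already records location (SAP 3.3.2).

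**If side must stay fixed.** Show Cohort 1's paired right-minus-left difference (mean, SD) for severity and Patient Bother beside those of Cohorts 3-6. Cohort 2 may be shown as a further reference with its assumption stated. Keep this descriptive and do not subtract Cohort 1: its estimate is too imprecise to serve as a correction. State in the SAP and report that I-BIS and S-BIS results cannot be separated from a side effect.

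Cost: SAP wording and a paired-difference column in two shells. Patient Bother also needs new mean and SD rows, or counts of subjects rated lower, equal or higher on the right.
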